# 4.4.2.2. Main Analytical Approach for Categorical Measures with Only 1 Postbaseline Measure

For the percentage of participants achieving improvement criteria from randomization at 72 week visit, a logistic regression model will be used.

A logistic regression model with terms of treatment group, stratification factors: baseline IGT (yes or no); baseline hyperlipidemia (based on TG; yes or no); baseline NAFLD (yes or no) and sex (female, male) as fixed effects. Baseline measurement will be included as a covariate if appropriate.

For measurement with only 1 postbaseline measure during the analysis period per schedule of activity, where LOCF approach will be applied to impute the endpoint when ED measure is available.

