2.3. Benefit/Risk Assessment

Because tirzepatide is a long-acting, GIP and GLP-1 receptor dual agonist, the potential risks associated with tirzepatide may be similar to the risks associated with currently available long-acting GLP-1 receptor agonists. The known risks associated with increased GLP-1 receptor activity include but are not limited to: GI effects (particularly nausea, vomiting, and diarrhea), hepatobiliary effects (gall bladder disease and hepatic safety), pancreatic safety, cardiovascular risk (heart rate and blood pressure), hypoglycemic events, thyroid safety, developmental safety, and allergic/hypersensitivity reactions.

More detailed information about the known and expected benefits and risks and reasonably expected AEs of tirzepatide may be found in the Investigator's Brochure.

Considering the measures taken to minimize risks to participants in this study, the identified potential risks in association with Study GPHZ are justified by the anticipated benefits that may be afforded to participants with obesity disease.

3. Objectives and Endpoints

Objectives	Endpoints		
Primary			
To demonstrate that once-weekly tirzepatide, at doses of 10 mg and/or 15 mg, is superior to placebo in terms of body weight reduction from BL to 72 weeks in Japanese participants with obesity disease	 Mean percent change in body weight at Week 72 and Proportion of participants who achieve ≥5% body weight reduction at Week 72 		
Secondary			
To compare the efficacy of once-weekly tirzepatide 10 mg and/or 15 mg with placebo for			
Improvement in obesity-related health problems (72 weeks)	 ○ Proportion of participants who met the following criteria at 72 weeks from BL ○ Improvement in at least 2 obesity-related health problems for participants with BL BMI ≥27 and <35 kg/m², or ○ Improvement in at least 1 obesity-related health problem for participants with BL BMI ≥35 kg/m² 		
Improvement in laboratory tests for obesity-related health problems (72 weeks)	 Mean changes in the following laboratory tests at 72 weeks from BL OGTT 2-hr glucose (only for participants with IGT at BL) Fasting glucose (only for participants with IGT at BL) Fasting lipids (TG) (only for participants with hyperlipidemia at BL) HFF (only for participants diagnosed as NAFLD by MRI at BL) 		
o Improvement of IGT (72 weeks)	 Proportion of participants who achieved improvements of IGT (only for participants with IGT at BL) 		

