## 4.4.3. Secondary and Exploratory Endpoints

Table GPHZ.4.2. Secondary and Exploratory Efficacy Measures for Improvement of Obesity-related Health Problems

Analysis variable	Criteria/Measures	Analysis set	Analysis method	Additional Information
Percentage of participants who met the following criteria at 72 weeks from BL	Improvement in at least 2 obesity related health problems for participants with BL BMI >27 and <35 kg/ m², or Improvement in at least 1 obesity related health problem for participants with BL BMI >35 kg/ m²	Efficacy analysis set	Logistic model in Section 4.4.2.2	Definition of endpoint: 4.4.1.3
	Improvement in at least 2 obesity-related health problems	Efficacy analysis set - participants with BL BMI ≥27 and <35 kg/m²	Logistic model in Section 4.4.2.2	Exploratory
	Improvement in at least 1 obesity-related health problem	Efficacy analysis set - participants with BL BMI ≥35 kg/m 	Logistic model in Section 4.4.2.2	Exploratory
Improvement in laboratory tests for obesity-related health problems (72 weeks)	Mean changes in OGTT 2-hr glucose at 72 weeks from BL	Efficacy analysis set - participants with IGT at BL	MMRM model in Section 4.3.2.1	
	Mean changes in fasting glucose at 72 weeks from BL	Efficacy analysis set - participants with IGT at BL	MMRM model in Section 4.3.2.1	
	Mean changes in Fasting lipids (TG) at 72 weeks from BL	Efficacy analysis set - participants with hyperlipidemia at BL	MMRM model in Section 4.3.2.1	
	Mean changes in HFF at 72 weeks from BL	Efficacy analysis set - participants diagnosed as NAFLD by MRI at BL	ANCOVA model in Section 4.4.2.1	
Improvement of IGT (72 weeks)	Proportion of participants who achieved improvements of IGT	Efficacy analysis set - participants with IGT at BL	Logistic model in Section 4.3.2.2	

Analysis variable	Criteria/Measures	Analysis set	Analysis method	Additional Information
Improvement of hyperlipidemia (72 weeks)	Proportion of participants who achieved improvements of hyperlipidemia	Efficacy analysis set - participants with hyperlipidemia at BL	Longitudinal logistic model in Section 4.4.2.3	
Improvement of NAFLD (72 weeks)	Proportion of participants who achieved improvements of NAFLD	Efficacy analysis set - participants diagnosed as NAFLD by MRI at BL	Logistic model in Section 4.3.2.2	Compare TZP 10 mg, 15 mg and pooled TZP doses with placebo

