# 5. Sample Size Determination

Approximately, 348 participants will be screened to achieve 261 randomly assigned to study intervention (approximately 87 participants per intervention group).

The sample size determination assumes that evaluation of superiority of tirzepatide 10 mg and tirzepatide 15 mg to placebo will be conducted in parallel, each at a 2-sided significance level of 0.025 using a 2-sample t-test. Additionally, a difference of at least 11% mean body weight percentage reduction from randomization at 72 weeks for tirzepatide 10 mg and/or tirzepatide 15 mg compared with placebo, a common SD of 10%, and a dropout rate of 25% are assumed for statistical power calculations. Under the assumptions above, randomizing 261 participants in a 1:1:1 ratio to tirzepatide 10 mg, tirzepatide 15 mg, and placebo provides more than 90% power to demonstrate superiority of each tirzepatide dose to placebo.

The chosen sample size and randomization ratio also provides >90% power to establish superiority of tirzepatide 10-mg and/or tirzepatide 15-mg doses to placebo in terms of proportion of participants achieving at least 5% body weight reduction at 72 weeks, conducted in parallel using a Fisher's exact test, each at a 2-sided significance level of 0.025, assuming 25% of placebo-treated participants and 90% of tirzepatide-treated participants achieve the goal and a dropout rate of 25%.

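### The first-listed secondary composite has a response rule that changes at baseline BMI 35 kg/m², but its logistic model does not name BMI class, which gives up some power

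*SAP*

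**What the plan says.** Protocol Section 3 lists the composite first among the secondary endpoints. Below BMI 35 kg/m² a participant needs at least two improvements. At or above it the bar is "Improvement in at least 1 obesity-related health problem for participants with BL BMI ≥35 kg/m²". SAP Table GPHZ.4.2 repeats this ("Improvement in at least 2 obesity related health problems for participants with BL BMI" 27 to 35 in the lower class) and sends the reader to SAP 4.4.1.3 for the definition and to SAP 4.4.2.2 for the model.

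SAP 4.4.2.2 specifies "A logistic regression model with terms of treatment group, stratification factors: baseline IGT (yes or no", followed by hyperlipidemia, NAFLD and sex. A baseline measurement may be added where appropriate, but BMI is not named. Protocol 9.4.3.2 has treatment and sex only. Randomisation is stratified by the three health problems and sex (SAP 1.2).

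The SAP's other two logistic specifications, 4.3.2.2 and 4.4.2.3, both carry baseline body weight.

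SAP 4.4.1.3 then defines a responder by problems still present after baseline: one or none in the lower BMI class, none in the higher class.

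**The concern.** BMI class is written into the definition of success, so it should predict response under either version of the rule. Yet the composite is assigned to the only logistic specification with neither weight nor BMI in it. Because BMI class is not a stratum, a chance imbalance between arms would go unadjusted. The optional baseline-measurement clause does not close the gap: a composite of glucose, triglyceride and liver-fat criteria has no single baseline measurement. What is at stake is power, and the precision of an absolute risk difference, on this one secondary comparison.

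**Working it through.** **1. The plan's own power figure.** SAP Section 5 gives "Approximately, 348 participants will be screened to achieve 261 randomly assigned to study intervention (approximately 87 participants per intervention group", "a difference of at least 11% mean body weight percentage reduction from randomization at 72 weeks" and "a common SD of 10%, and a dropout rate of 25% are assumed for statistical power calculations", tested "each at a 2-sided significance level of 0.025 using a 2-sample t-test".

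- Evaluable per arm: 87 × 0.75 = 65.25, taken as 65.
- Standardised difference: 11 / (10 × √(2/65)) = 6.27. The two-sided 0.025 critical value is 2.24.
- Power = Φ(6.27 − 2.24) = Φ(4.03) = 0.99997 (0.99996 by the t-test).
- Fisher's exact test at 25% versus 90%: above 0.9999.

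The stated power above 90% is reproduced. It concerns the weight endpoints only. The documents give no power, response rate or BMI split for the composite.

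**2. The two rules side by side.** Improvements needed to respond, assuming an improved problem no longer counts and none is newly acquired:

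| Baseline BMI | Problems at entry | Endpoint wording | Responder rule (SAP 4.4.1.3) |
|---|---|---|---|
| <35 | 2 | 2 | 1 |
| <35 | 3 | 2 | 2 |
| ≥35 | 1 | 1 | 1 |
| ≥35 | 2 | 1 | 2 |
| ≥35 | 3 | 1 | 3 |

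Among participants with the same two or three problems, the bar differs by BMI class under both rules, but in opposite directions. Terms for the three problems therefore cannot stand in for BMI class.

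**3. Closed form, at the null.** With a share w at BMI ≥35 and response rates p₀ and p₁ in the two classes, the fraction of effective sample size lost by omitting the class is w(1−w)(p₁−p₀)² / [p̄(1−p̄)].

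- w = 0.3, rates 0.3 and 0.7: 0.21 × 0.16 / (0.42 × 0.58) = 0.138.
- w = 0.2, rates 0.5 and 0.6: 0.16 × 0.01 / (0.52 × 0.48) = 0.006.
- Over w of 0.2 to 0.5 and gaps of 10 to 40 points, the loss is 0.6% to 16%.

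**4. Simulation.** There were 1,500 two-arm trials per setting, tested at two-sided 0.05 (SAP 4.1), with the 4.4.2.2 terms fitted with and without BMI class. All clinical inputs are assumptions, given in the order IGT, hyperlipidemia, NAFLD:

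- prevalence before the eligibility rule: 68%, 80%, 70%;
- improvement on placebo: 0.25, 0.35, 0.20;
- improvement on drug: 0.45, 0.55, 0.40 (moderate) or 0.80, 0.75, 0.75 (large);
- shared normal frailty with SD 0.8 on the logit scale, and 60% in one sex category.

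The sample-size factor is the squared ratio of the empirical SDs of the standardised risk difference (without BMI class / with it). Results for the moderate effect:

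| Rule | Per arm | Share ≥35 | Power without → with | Sample-size factor |
|---|---|---|---|---|
| Improved | 87 | 25% | 0.782 → 0.835 | 1.118 |
| Improved | 87 | 45% | 0.755 → 0.822 | 1.182 |
| Improved | 65 | 25% | 0.640 → 0.694 | 1.107 |
| Improved | 65 | 45% | 0.633 → 0.693 | 1.192 |
| Remaining | 87 | 25% | 0.787 → 0.833 | 1.131 |
| Remaining | 87 | 45% | 0.750 → 0.811 | 1.156 |
| Remaining | 65 | 25% | 0.661 → 0.713 | 1.086 |
| Remaining | 65 | 45% | 0.621 → 0.678 | 1.149 |

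A factor of 1.09 to 1.19 means that omission forgoes 1 − 1/1.09 = 8% to 1 − 1/1.19 = 16% of effective sample size.

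For the large effect the factor is 1.09 to 1.15, but power is 0.999 to 1.000 either way (for example, mean z 6.10 → 6.12). Across all settings the standard error of the log-odds ratio rises by 7 to 19% and the log-odds ratio rises with it (for example, 0.374 → 0.426 and 2.30 → 2.63).

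Simulated placebo response (<35 / ≥35, with 25% at ≥35) is 0.16 / 0.50 under the improved rule and 0.36 / 0.12 under the remaining rule.

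**5. Second set of assumptions.** Here there are 87 per arm, 30% or 45% at BMI ≥35, and each problem improves with probability 0.25 on placebo and 0.40 on drug. Power goes from 0.66 to 0.75 and from 0.64 to 0.74 under the improved rule, and from 0.64 to 0.70 and from 0.61 to 0.68 under the remaining rule. Under the null, rejection is 0.044 to 0.056 with or without the term.

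**The case against.** The strongest reply is that little may depend on this. The plan's only responder assumption is "assuming 25% of placebo-treated participants and 90% of tirzepatide-treated participants achieve the goal and a dropout rate of 25", for weight loss. If the composite separated as widely, power would be saturated: at 0.25 versus 0.60 per problem it is already 0.998 to 1.000 at 87 per arm, and 0.992 to 0.997 at 65, without BMI class. That stands, but the plan states no expected effect for the composite, so a large one cannot be presumed.

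Table GPHZ.4.2 also plans the same model within each BMI class as exploratory rows. Those rows split the sample and do not adjust the overall comparison.

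It can also be said that choosing a covariate is premature while the two rules disagree. The disagreement is real, but a fixed effect assumes no direction and BMI class is prognostic under both.

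A reader might infer three stronger things that the documents do not support:

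- **That this is a key secondary endpoint.** It is only listed first. Multiplicity control covers the weight hypotheses alone (SAP 2.1).
- **That the odds ratio is biased.** The models with and without BMI class target different conditional odds ratios. Under randomisation, omission causes neither bias nor type I error inflation.
- **That the odds ratio would gain precision.** Its standard error on the log scale goes up. The gain appears in power and in the standardised risk difference.

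**Conclusion.** The point holds as one of efficiency. The composite's rule depends on baseline BMI class, and its model does not name it. Under the stated assumptions, adding the term is worth about 9 to 19% in effective sample size on the risk-difference scale. It adds about 5 to 10 points of power when the effect is moderate and essentially none when it is large. None of these sizes can be derived from the documents, which give neither response rates nor a BMI split for this endpoint. The validity of the analysis and the co-primary results are unaffected. The conflict between endpoint wording and responder rule is a separate matter that needs no assumptions about rates: the two rules classify some participants differently and reverse which BMI class faces the stricter bar.

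**What to change.** For the composite row of Table GPHZ.4.2, add baseline BMI class (<35, ≥35 kg/m²) as a fixed effect to the 4.4.2.2 model, in place of reliance on the optional baseline-measurement clause. Report a covariate-standardised risk difference with its confidence interval beside the odds ratio; this matches the difference in response percentages that SAP 1.1.2.1 uses as its summary for the responder endpoint.

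Separately, reconcile the endpoint wording (Protocol Section 3, SAP 4.4.1.3 and Table GPHZ.4.2) with the responder definition in SAP 4.4.1.3, so that a single rule is programmed.

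The cost is one model term and one degree of freedom. No new data are needed: the same BMI split is already planned for subgroups (SAP 4.6.3.1) and baseline tables (SAP 6.1.1).

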#### 4.4.2.3. Analytical Approach for Binary Outcome with Repeated Measures

For some binary outcomes, longitudinal logistic regression with repeated measurements will be used with the independent variables of analysis model are treatment group, visit, and treatment-by-visit interaction, stratification factors: baseline IGT (yes or no); baseline hyperlipidemia (based on TG; yes or no); baseline NAFLD (yes or no) and sex (female, male) as fixed effects, and baseline body weight as a covariate.

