#### 4.3.2.2. Main Analytical Approach for Categorical Measures

For the percentage of participants achieving at least 5% body weight reduction from randomization over time, a logistic regression model will be used with the response variable of the percentage of participants achieving at least 5% body weight reduction at each scheduled postbaseline visit.

A logistic regression model with terms of treatment group stratification factors: baseline IGT (yes or no); baseline hyperlipidemia (based on TG; yes or no); baseline NAFLD (yes or no) and sex (female, male) as fixed effects, and baseline body weight as a covariate, will be conducted for percentage of participants achieving at least 5% body weight reduction from randomization at the 72 week visit. Missing body weight measurement at 72 week will be imputed by the predicted value from MMRM model aforementioned, then the continuous measurements will be dichotomized into status of achieving at least 5% body weight reduction (Yes or No). A logistic regression will be utilized to analyze proportion of participants with at least 5% body weight reduction at each nominal visit from randomization through 72 weeks.

With the aid of the logistic regression model, 2-sided 95% CI and odds ratio for percentage of participants achieving at least 5% body weight reduction from baseline to the 72-week visit between tirzepatide 10 mg or 15 mg QW and placebo will be derived.

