Percentage of participants who met the following criteria at 72 weeks from BL	Improvement in at 2 or 3 obesity related health problems	Efficacy analysis set - participants with 3 defined obesity-related health problems	Logistic model in Section 4.3.2.2	Exploratory
	Improvement in at 2 obesity related health problems	Efficacy analysis set - participants with 2 defined obesity-related health problems	Logistic model in Section 4.3.2.2	Exploratory
	Improvement in at 1 obesity related health problems	Efficacy analysis set - participants with 3 defined obesity-related health problems	Logistic model in Section 4.3.2.2	Exploratory

Abbreviations: ANCOVA = analysis of covariance; BL = baseline; BMI = body mass index; IGT = impaired glucose tolerance; MMRM = mixed model for repeated measures; NAFLD = non-alcoholic fatty liver disease; OGTT = oral glucose tolerance test; TG = triglycerides; TZP = tirzepatide.

Table GPHZ.4.3. Secondary and Exploratory Efficacy Measures for Body Mass

Analysis variable	Criteria/Measures	Analysis set	Analysis method	Additional Information
Change in body weight (24, 52, and 72 weeks)	Proportion of participants who achieve the following criteria from BL	Efficacy analysis set	Logistic model in Section 4.3.2.2	
	
 
≥5% body weight reduction (only at 24 and 52 weeks)
 
≥7% body weight reduction
 
≥10% body weight reduction
 
≥15% body weight reduction
 
≥20% body weight reduction
 
			
	Mean percent change from BL in  • Body weight (%) (Only at 24 and 52 weeks)	Efficacy analysis set	MMRM model in Section 4.3.2.1	
	Mean change from BL in			
	

Absolute body weight (kg)

BMI

			
EWL	EWL defined in Section 4.4.1.1	Efficacy analysis set	MMRM model in Section 4.3.2.1	
Change in VAT and SAT (72 weeks)	Mean change from BL in  VAT area (cm²)  SAT area (cm²)  VAT/SAT ratio	Efficacy analysis set	ANCOVA model in Section 4.4.2.1	
	Mean percent change from BL in  VAT area (cm²)  SAT area (cm²)  VAT/SAT ratio	Efficacy analysis set	ANCOVA model in Section 4.4.2.1	

Analysis variable	Criteria/Measures	Analysis set	Analysis method	Additional Information
	Proportion of participants who achieve VAT <100 cm 	Efficacy analysis set - participants with VAT ≥100 cm² at	Logistic model in Section 4.4.2.2	
Change in waist circumference (24, 52, and 72 weeks)	Mean change from BL in waist circumference	BL Efficacy analysis set	MMRM model in Section 4.3.2.1	

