# 4.7. Other Exploratory Analyses

Exploratory analyses in this section will not be used for the CSR/CTD, but for the other purpose (eg. the publication).

To describe subject status regarding 3 defined ORHPs (IGT, hyperlipidemia and NAFLD) from baseline to Week 72, a Sankey diagram will be generated.

Scatter plot of creatinine and change in BMI (or body weight (kg)) will be created.

To explore relationships between change in PRO and the percentage of participants achieving at least 5% (and 7%, 10%, 15% or 20%) body weight reduction at 72 weeks, cross tabulation may be generated. PRO items include:

- SF36v2, acute form
  - Mental Component Summary (MCS)
  - Physical Component Summary (PCS)
  - Physical Functioning domain (PF)

- IWQOL-Lite-CT
  - Total score
  - Physical function composite score
  - o physical score
  - o Psychosocial composite score

The Analysis for achievement of ALT ≤30 U/L using longitudinal logistic regression model in Section 4.4.2.3 will be provided.

The analysis of the change in NFS (NAFLD fibrosis score) will be conducted.

• NFS =  $-1.675 + 0.037 \times age + 0.094 \times BMI (kg/m^2) + 1.13 \times IFG/diabetes (yes=1, no=0) + 0.99 \times AST/ALT - 0.013 \times blood platelet (<math>\times 10^9/L$ ) -  $0.66 \times albumin (g/dL)$ . (Tokushige et al. (2020))

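### SAP 4.4.2.3 omits the outcome's own baseline, and Table GPHZ.4.2 sends single-scan NAFLD improvement to a section whose imputation is written for body weight

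*SAP*

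**What the plan says.** **Covariates.** SAP 4.4.2.3 lists treatment, visit, treatment-by-visit and the four stratification factors, ending with "baseline NAFLD (yes or no) and sex (female, male) as fixed effects, and baseline body weight as a covariate". Three analyses use it. Hyperlipidemia improvement (Table GPHZ.4.2) and hyperuricemia improvement (Table GPHZ.4.4) both cite "Longitudinal logistic model in Section 4.4.2.3". Section 4.7 adds "achievement of ALT ≤30 U/L using longitudinal logistic regression model in Section 4.4.2.3", and says at its start that its analyses are not for the CSR/CTD. By contrast, 4.4.2.1 always includes the outcome's own baseline, and 4.4.2.2 includes it where appropriate.

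**Routing.** In Table GPHZ.4.2 the NAFLD improvement row cites "Logistic model in Section 4.3.2.2". The only imputation step in that section is "Missing body weight measurement at 72 week will be imputed by the predicted value from MMRM model aforementioned", followed by dichotomising. Mean change in HFF cites "ANCOVA model in Section 4.4.2.1". The composite (Table GPHZ.4.2) and VAT <100 cm² (Table GPHZ.4.3) cite "Logistic model in Section 4.4.2.2". Sections 4.4.2.1 and 4.4.2.2 both apply LOCF from an ED measure to outcomes with a single post-baseline measure. The exploratory rows that count improvements by number of baseline problems, such as "Improvement in at 2 or 3 obesity related health problems", return to 4.3.2.2.

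**General rule.** SAP 4.1 sends missing Week 72 values in primary and secondary efficacy analyses to the Section 4.3.2 method. Its next sentence, opening with an otherwise, gives LOCF to parameters with only one post-baseline measure.

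**The concern.** A cut-off outcome depends heavily on where the participant started. Body weight is a weak stand-in for baseline triglyceride, uric acid or ALT. The stratification factors do not fill the gap: hyperlipidemia status is constant in a subset defined by measured triglyceride (SAP 4.4.1.2).

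The routing matters more. NAFLD improvement is a named secondary endpoint, yet a programmer could take its missing-data rule from 4.3.2 or from the LOCF exception and cite SAP 4.1 for either. One scan result could then be carried forward for mean HFF and the composite, but predicted or left missing for NAFLD improvement and the count rows. An open choice that can move a treatment difference should be closed before database lock.

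**Working it through.** **1. The plan's own figure.** With 25% dropout, 87 × 0.75 ≈ 65 per arm. For a difference of 11, SD 10 and two-sided 0.025, the noncentrality is 1.1/√(2/65) = 6.27, and t-test power is 99.996%. Fisher power for 25% versus 90% exceeds 99.9999%. The stated figure of more than 90% reproduces, and nothing below touches it.

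**2. The rows side by side.** Protocol Table 2 schedules MRI-PDFF after baseline only at Visit 21, and OGTT and lipids at Weeks 24, 52 and 72.

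| Outcome | SAP section | Own baseline | Missing Week 72 value |
|---|---|---|---|
| NAFLD improvement | 4.3.2.2 | no | section text covers body weight only |
| Mean change in HFF | 4.4.2.1 | yes | LOCF from ED |
| VAT <100 cm² | 4.4.2.2 | if appropriate | LOCF from ED |
| Composite | 4.4.2.2 | if appropriate | HFF by LOCF; OGTT and TG by 4.3.2, through 4.1 |
| Count rows (exploratory) | 4.3.2.2 | no | section text covers body weight only |

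**3. How many scans are at issue.** The protocol requires more than 40% of participants to have NAFLD: 0.40 × 261 / 3 = 34.8, so about 35 per arm as a floor. Applying the sizing dropout, 0.25 × 35 = 8.75, about 9 missing per arm. An ED scan needs 36 weeks of exposure (Protocol Table 3) and must fall within last dose + 14 days (SAP Table GPHZ.3.2). Assume 1/3 to 2/3 of dropouts reach 36 weeks and 1/2 to all of those scans fall inside the window:
- low: 8.75 × 1/3 × 1/2 = 1.5 per arm (4% of 35)
- high: 8.75 × 2/3 × 1 = 5.8 per arm (17% of 35)

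**4. Effect of predicting HFF and then dichotomising.** Assumed: 35 per arm, 9 missing at random per arm, log-normal HFF with median 13, carry-over slope 0.6, 30% of placebo improved, no ED scans. True differences of 25, 30, 45 and 60 points came out as 31, 39, 55 and 67. A second run on assumed inputs gave 31, 38, 55 and 67. Complete cases were within 0.3 point of truth.

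The mechanism can be checked by hand. The observed difference is (26/35) × true + (9/35) × G, where G is the gap among imputed participants. For the first case, G = (35 × 31 − 26 × 25)/9 = 48 points; the other three give 65, 84 and 87. A single predicted value has no residual spread, so most missing tirzepatide participants fall on the improved side and most missing placebo participants on the other.

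Against LOCF, separate simulations gave increases of 2 to 8 points (27 to 29, 35 to 39, 48 to 56, 64 to 71) and a nominal SE 8 to 19% smaller. That contrast depends on how many ED scans exist and what they show, which the documents do not give.

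**5. Power gained by adding own baseline to body weight.** Logistic simulation of the Week 72 outcome alone: 2,000 trials per setting, two-sided 0.05, carry-over slopes 0.3 to 0.8, body weight correlating 0 to 0.3 with the outcome. Response rates, distributions and subset sizes are assumed. Monte Carlo SE is about 1 point per power.

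| Outcome | Per arm (without, with dropout) | Change in power, points |
|---|---|---|
| Hyperlipidemia | 50, 38 | −0.5 to +2.4 |
| Hyperuricemia | 30, 23 | +0.4 to +8.0 |
| ALT ≤30, slope 0.3 | 87, 65 | +2 to +3 |
| ALT ≤30, slope 0.6 | 87, 65 | +9 to +11 |
| ALT ≤30, slope 0.8 | 87, 65 | +19 to +24 |

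A repeat for ALT at 65 per arm moved power from 62 to 65, 65 to 76 and 62 to 87 at the three slopes (+3, +11 and +25). Limiting ALT to baseline above 30 gave 0 to +14. Replacing body weight instead of adding to it gave −6.3 to +2.0 for hyperlipidemia, so the term should be added.

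**The case against.** Adjusting for body weight is valid, and it follows the protocol's longitudinal logistic model for the co-primary endpoint (Protocol 9.4.3.1). The only secondary endpoint under 4.4.2.3 gains almost nothing. The large gains belong to an ALT analysis that will not enter the CSR/CTD. The simulations use one visit, whereas 4.4.2.3 is a repeated-measures model. All of that stands.

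On NAFLD, HFF is not assigned to any MMRM, so 4.3.2.2 read literally yields no predicted HFF, and the single-measure exception in SAP 4.1 fits it naturally. That makes LOCF the more sensible reading. It does not make it the only one, because the row cites 4.3.2.2 and the first rule in 4.1 names secondary endpoints.

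A reader might infer that the composite has no rule for a missing OGTT or TG value. The documents do not support that: the composite is secondary, 4.1 sends it to the 4.3.2 method, and fasting glucose, 2-hour glucose and TG are already modelled by MMRM. The difficulty is only that the composite row itself cites 4.4.2.2.

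**Conclusion.** The point holds as two separate defects of wording. The missing baseline term costs precision in one secondary and two exploratory analyses: near zero for hyperlipidemia and larger for the pure cut-off outcomes, most of all ALT ≤30, which is not restricted to baseline ALT above 30. The NAFLD row points to an imputation that does not fit a single scan. On assumed inputs, the less suitable reading overstates the responder difference by about 6 to 10 points. The composite and count rows can also treat the same missing HFF result differently.

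The cross-references are certain. The sizes are illustrations, since the documents give no distributions, carry-over slopes or response rates for these outcomes. Three stronger inferences fail. The tests are not invalid. The co-primary analyses, and the type I error control that covers only H10 and H15, are untouched. Multiple imputation is not required to resolve the routing. SAP 4.9 does not list the move from the treatment-and-sex model of Protocol 9.4.3.2, but that is record-keeping and not part of this defect.

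**What to change.** - **SAP 4.4.2.3:** keep baseline body weight and add the baseline value of the measure that defines the outcome (TG, uric acid or ALT).
- **Table GPHZ.4.2, NAFLD improvement:** cite 4.4.2.2, with baseline HFF as covariate and LOCF from an ED scan inside the imaging EAS window (last dose + 14 days).
- **SAP 4.1:** state that single-scan outcomes (HFF, VAT, SAT) follow LOCF and that Section 4.3.2 does not apply to them.
- **Individual, composite and count rows:** derive each participant's IGT, TG and HFF status once and use it in every row.

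The cost is SAP wording, some programming and one more model term in small subsets. The baseline values and ED scans are already in the schedule.
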